### **5.2.2 Summary of Nonclinical Studies in NASH**

One nonclinical study with elobixibat in a NASH model has been completed. The study evaluated the effects of elobixibat in leptin-deficient ob/ob mice treated with a diet high in trans fats, fructose, and cholesterol. Although elobixibat did not reduce liver NAFLD activity score or fibrosis stage, there were indicators of relevant effects, including reduction in liver alpha-smooth muscle actin ( $\alpha$ -SMA), which is a marker of stellate cell activation and thereby an indirect marker for fibrosis formation. Administration of 10 and 30 mg/kg/day elobixibat decreased liver steatosis as quantified by lipid fractional area in hematoxylin and eosin (H&E)-stained liver sections in a dose-dependent fashion. This was further evident in animals treated with 30 mg/kg elobixibat that showed reduced liver triglycerides and liver total cholesterol as determined by biochemical analyses. Analysis of liver gene expression by next generation RNA sequencing revealed pronounced and dose-dependent effects of elobixibat. It affected the expression of genes in key pathways associated with NASH pathology.

Additional nonclinical studies with elobixibat are summarized in the Investigator's Brochure ([M1.14.4.1](#)).

### **5.3 Rationale**

Bile acids act as signaling molecules in lipid, glucose, and energy homeostasis. Studies have shown that both serum and liver bile acids are increased in patients with NASH

([Ferslew 2015](#)), and recent data have suggested that the presence and severity of NASH is associated with specific changes in circulating bile acids ([Puri 2018; Sanyal 2018](#)). Inhibition of bile acid absorption from the intestine has the potential to improve the pathophysiology in NASH, including the related cardiovascular and metabolic disease due to impingement on multiple key metabolic feedback mechanisms, as follows: lowering of LDL-C by increased bile acid synthesis, and improving insulin sensitivity by increasing GLP-1 levels. A reduction of cardiovascular risk is particularly desirable for any pharmacological NASH treatment, because cardiovascular complications contribute to a significant amount of mortality in patients with NAFLD/NASH, with their annual risk being 2-fold increased ([Mahfood Haddad 2017; Younossi 2018](#)). IBAT inhibition reduces the levels of bile acid that circulate to the liver, and triggers increased hepatic bile acid synthesis from cholesterol. Thus, besides having a positive impact on cardiovascular health, IBAT inhibition might also reduce hepatic cell damage by lowering free cholesterol and changing the composition of toxic bile acids in the liver.

#### 5.4 Risk/Benefit

Elobixibat is orally administered and acts locally in the gut where it binds reversibly to the IBAT to decrease the reuptake of bile acids into the liver, thereby increasing the concentration of bile acids in the colon. Due to its mechanism of action, most adverse events (AEs) are gastrointestinal (GI) tract disorders, such as abdominal pain, diarrhea, abdominal distention, flatulence, and nausea; the incidence of these has increased with increasing dose levels. Diarrhea has been the most prominent dose-limiting side effect. No clinically significant findings in laboratory measures or electrocardiograms (ECGs) have been reported. Based on postmarketing case reporting, ischemic colitis will be monitored as an adverse event of special interest for elobixibat.

There is no established benefit for subjects participating in this Phase 2 study. Based upon these data, the risk/benefit for subjects participating in this trial is acceptable.

This study will be conducted in compliance with the protocol and with the International Council on Harmonisation (ICH) guidelines on GCP.

## **6. STUDY OBJECTIVES**

### **6.1 Primary Objective**

The primary objective is to evaluate the efficacy of repeated once-daily doses of 5 mg elobixibat on serum levels of LDL-C in patients with NAFLD or NASH.

### **6.2 Secondary Objectives**

- To assess the safety and tolerability of elobixibat in patients with NAFLD or NASH
- To evaluate the effect of elobixibat on liver steatosis as measured by magnetic resonance imaging (MRI) for (i) liver fat fraction (using proton density fat fraction [PDFF]) and (ii) total liver fat (using whole liver fat volume)
- To evaluate the effect of elobixibat on liver function using alanine aminotransferase (ALT)
- To evaluate the effect of elobixibat on lipids and total bile acids (BA) in patients with NAFLD or NASH

## 7. INVESTIGATIONAL PLAN

### 7.1 Overall Study Design and Plan

#### 7.1.1 Description

This is a double-blind, randomized, placebo-controlled, Phase 2 study to explore the efficacy and safety of elobixibat (oral dose of 5 mg) once daily for 16 weeks in patients with NAFLD or NASH. The study includes a 6-week Screening Period, followed by a 16-week Treatment Period, and a Follow-Up Visit 2 weeks after the last dose of study drug.

After completing the Screening Period, eligible patients will be randomized on Day 1 (Visit 2) in a 1:1 fashion to either 5 mg/day elobixibat or matching placebo. Visit windows applicable to each visit are presented in the schedule of assessments ([Table 1](#)). There will be up to 7 clinic visits during the study, as follows:

- Visit 1: Screening period (Week -6 through Day -1)
- Visit 2: Day 1/Randomization visit
- Visit 3: Week 4
- Visit 4: Week 8
- Visit 5: Week 12
- Visit 6: Week 16/End of Treatment (EOT). Any patient that discontinues treatment prematurely should complete this visit at the time of discontinuation
- Visit 7: Follow-Up period. The Follow-Up visit will occur 2 weeks after the last dose of study drug whether the patient completes the study or discontinues prematurely

Additional unscheduled visits may be required for patients who need direct site assistance (due to AE monitoring, in order to fulfill screening requirements, and/or for safety maintenance).

Patients who screen fail may be rescreened if approved by Sponsor's Medical Monitor.

**7.1.1.1                    Screening Period**

Informed consent must be obtained at Visit 1 prior to performing any study procedures. After signing the informed consent form (ICF), patients will be considered enrolled and evaluated for study eligibility.

**7.1.1.2                    Treatment Period**

Eligibility for randomization will be determined at Visit 2 using the assessment of eligibility in accordance to the inclusion/exclusion criteria.

The patient will return to the clinic at Visits 3-6 for assessments. Patients will be requested to return study drug bottles as part of drug accountability during the Treatment period.

**7.1.1.3                    Follow-Up Period**

The patient will return to the clinic for Visit 7 approximately 2 weeks after the last dose of study drug. This visit will be completed for patients that discontinue treatment prematurely.

**7.1.1.4                    End of Study**

The end of the study is defined as last patient last visit (LPLV) and all sites are closed.

**7.1.2                    Schedule of Assessments**

The schedule of assessments is presented in [Table 1](#).

**Table 1** Schedule of Assessments

VISIT	SCREENING PERIOD	TREATMENT PERIOD					FOLLOW-UP PERIOD
	VISIT 1	VISIT 2/ RANDOMIZA- TION	VISIT 3	VISIT 4	VISIT 5	VISIT 6/ END OF TREATMENT	VISIT 7
STUDY WEEK	WEEK -6 TO DAY -1	DAY 1	WEEK 4	WEEK 8	WEEK 12	WEEK 16	WEEK 18
VISIT WINDOW			±3 DAYS	±3 DAYS	±3 DAYS	±3 DAYS	±3 DAYS
Informed consent	X						
Inclusion/exclusion criteria	X	X					
Medical/surgical history f	X						
Demographics	X						
Serology a	X						
12-lead ECG	X					X	
Physical examination b	X	X				X	
Vital signs c	X	X	X	X	X	X	X
Pregnancy test d	X	X	X	X	X	X	X
MRI e	X					X	
Randomization g		X					
Clinical safety laboratory tests h	X	X	X	X	X	X	X

(Continued on next page)

VISIT	SCREENING PERIOD	TREATMENT PERIOD					FOLLOW-UP PERIOD
		VISIT 1	VISIT 2/ RANDOMIZA- TION	VISIT 3	VISIT 4	VISIT 5	
STUDY WEEK	WEEK -6 TO DAY -1	DAY 1	WEEK 4	WEEK 8	WEEK 12	WEEK 16	WEEK 18
VISIT WINDOW			±3 DAYS	±3 DAYS	±3 DAYS	±3 DAYS	±3 DAYS
Endocrinology h	X	X	X			X	
GLP-1, FGF-19, C4 h	X	X	X	X	X	X	X
Total bile acids h	X	X	X	X	X	X	X
Lipid profile h	X	X	X	X	X	X	X
Fibrosis and inflammation markers h		X	X			X	
High-sensitivity CRP	X		X			X	
Stored blood sample for future testing i	X	X	X	X	X	X	X
Dispense study drug		X	X	X	X		
Review alcohol consumption j	X						
Review concomitant medications	X	X	X	X	X	X	X
Review adverse events	X	X	X	X	X	X	X

a Includes hepatitis B virus surface antigen and hepatitis C virus antibody and RNA

b Includes height (at Screening only), weight, waist circumference, and waist-to-hip ratio. Body mass index will be calculated based on height and weight. A full physical examination will be performed at Screening and at Visits 2 and 6.

c Vital signs include blood pressure, heart rate, respiratory rate, and oral body temperature.

(Continued on next page)

d For women of childbearing potential, a serum pregnancy test will be performed at Screening, and a urine pregnancy test will be performed at each visit at which study drug is dispensed.

e Patients will have MRI to measure liver fat (PDFF), and total liver volume. Patients who discontinue before Visit 6 (Week 16) should have an MRI performed at End of Treatment if they completed at least 4 weeks of treatment.

f Liver biopsy results for confirmed NASH within 6 months of Screening to confirm patient eligibility will be collected in the eCRF, if available.

g Randomization will occur at Visit 2 to assign patients to either 5 mg/day elobixibat or placebo in 1:1 ratio.

h See [Table 2](#), Laboratory Parameters. Clinical safety laboratory tests include clinical chemistry, hematology/coagulation, and urinalysis

i See Section [9.2.4](#).

j History of alcohol consumption will be obtained at Screening.

**Abbreviations:** C4: 7 $\alpha$ -hydroxy-4-cholesten-3-one; CRF: case report form; CRP: C-reactive protein; ECG: electrocardiogram; EOT: End of Treatment; FGF-19: fibroblast growth factor-19; GLP-1: glucagon-like peptide-1; INR: international normalized ratio; MRI: magnetic resonance imaging; NASH: nonalcoholic steatohepatitis; PDFF: proton density fat fraction

### **7.1.3 Study Procedures and Assessments**

#### **7.1.3.1 Screening Period (-6 Weeks to Day -1)**

##### **7.1.3.1.1 Visit 1**

Patients will undergo a Screening visit up to 6 weeks prior to the planned first day of study treatment. Screening procedures and assessments are as follows:

- Obtain written informed consent
- Assess inclusion/exclusion criteria (Sections [7.2.1](#) and [7.2.2](#), respectively)
- Medical and surgical history (date of diagnosis of NAFLD/NASH including liver biopsy results for biopsy-confirmed NASH patients within 6 months of screening; any surgery performed; any other diagnosis)
- Record demographics (age, full date of birth, gender, race, and ethnicity)
- Serology
- 12-lead ECG (Section [10.2.6](#))
- Physical examination (Section [10.2.4](#))
- Vital signs (Section [10.2.5](#))
- Pregnancy test
- MRI (Section [9.2.2](#))
- Clinical safety laboratory tests (Section [10.2.1](#))
- Endocrinology (Section [10.2.1](#))
- GLP-1, FGF-19, C4 (Section [10.2.1](#))
- Total BA (Section [9.2.3](#))
- Lipid profile (Section [9.2.1](#))
- Fibrosis and inflammation markers (Section [10.2.1](#))

- High-sensitivity CRP
- Stored sample for future testing (Section 10.2.1)
- Review of alcohol consumption
- Document concomitant medications
- AE monitoring

### **7.1.3.2 Treatment Period (Day 1 to Week 16)**

#### **7.1.3.2.1 Study Day 1/Visit 2 (Randomization)**

At the randomization visit, the following assessments will be conducted:

- Review inclusion/exclusion criteria (Sections 7.2.1 and 7.2.2, respectively)
- Physical examination (Section 10.2.4)
- Vital signs (Section 10.2.5)
- Pregnancy test
- Clinical safety laboratory tests (Section 10.2.1)
- Endocrinology (Section 10.2.1)
- GLP-1, FGF-19, C4 (Section 10.2.1)
- Total BA (Section 9.2.3)
- Lipid profile (Section 9.2.1)
- Fibrosis and inflammation markers (Section 10.2.1)
- Stored sample for future testing (Section 10.2.1)
- Study drug is dispensed and patients are instructed to administer daily from Day 1
- Review of concomitant medications
- AE monitoring

### **7.1.3.2.2 Study Weeks 4-12/Visits 3-5**

The following procedures and assessments will be conducted:

- Vital signs (Section 10.2.5)
- Pregnancy test
- Clinical safety laboratory tests (Section 10.2.1)
- Endocrinology (Visit 3 only; Section 10.2.1)
- GLP-1, FGF-19, C4 (Section 10.2.1)
- Total BA (Section 9.2.3)
- Lipid profile (Section 9.2.1)
- Fibrosis and inflammation markers (Visit 3 only; Section 10.2.1)
- High-sensitivity CRP (Visit 3 only; Section 10.2.1)
- Stored sample for future testing (Section 10.2.1)
- Study drug is dispensed; review of compliance
- Review of concomitant medications
- AE monitoring

### 7.1.3.2.3 Study Week 16/Visit 6/EOT

The last dose of study drug will be taken in the morning the day before Visit 6 and the following procedures and assessments will be conducted (also conducted at the time a patient prematurely withdraws):

- 12-lead ECG (Section 10.2.6)
- Physical examination (Section 10.2.4)
- Vital signs (Section 10.2.5)
- Pregnancy test
- MRI (Section 9.2.2)

- Clinical safety laboratory tests (Section 10.2.1)
- Endocrinology (Section 10.2.1)
- GLP-1, FGF-19, C4 (Section 10.2.1)
- Total BA (Section 9.2.3)
- Lipid profile (Section 9.2.1)
- Fibrosis and inflammation markers (Section 10.2.1)
- High-sensitivity CRP
- Stored sample for future testing (Section 10.2.1)
- Review of concomitant medications
- AE monitoring

### 7.1.3.3 Follow-Up Period

#### 7.1.3.3.1 Study Week 18/ Visit 7

All patients will complete a Follow-Up visit approximately 2 weeks after the last dose of study drug for the following assessments:

- Vital signs (Section 10.2.5)
- Pregnancy test
- Clinical safety laboratory tests (Section 10.2.1)
- GLP-1, FGF-19, C4 (Section 10.2.1)
- Total BA (Section 9.2.3)
- Lipid profile (Section 10.2.1)
- Stored sample for future testing (Section 10.2.1)
- Review of concomitant medications
- AE monitoring

## 7.2 Study Population

A total of approximately 46 patients with a clinical diagnosis of NAFLD/NASH (in accordance with the protocol definition) will be randomized.

### 7.2.1 Inclusion Criteria

Patients must meet all the following criteria to be included in the study:

1. Be willing to participate in the study and provide written informed consent
2. Be a man or woman  $\geq 18$  years of age
3. Have a current biopsy-confirmed NASH within 6 months of screening **or** a suspected diagnosis of NAFLD/NASH based on the criteria outlined below:
  - a. Biopsy-confirmed NASH is defined as histological NASH diagnosis with fibrosis stage F1 through F3 and a NAFLD activity score (NAS) of  $\geq 4$  with a score of  $\geq 1$  in each of the NAS components below as assessed by the central pathologist using the NASH Clinical Research Network criteria ([Kleiner 2005](#))
    - i. Steatosis (scored 0 to 3)
    - ii. Ballooning degeneration (scored 0 to 2)
    - iii. Lobular inflammation (scored 0 to 3)

### OR

- b. The suspected diagnosis of NAFLD/NASH is based on the diagnosis of metabolic syndrome as having any 3 of the following 5 risk factors at Screening:
  - i. Fasting plasma glucose  $\geq 100$  mg/dL or undergoing drug treatment for elevated glucose
  - ii. High-density lipoprotein-cholesterol (HDL-C)  $<40$  mg/dL in males or  $<50$  mg/dL in females or undergoing drug treatment for reduced HDL-C

- iii. Triglycerides  $\geq 150$  mg/dL or undergoing drug treatment for elevated triglycerides
- iv. Waist circumference  $>102$  cm in males or  $>88$  cm in females
- v. Systolic blood pressure  $\geq 130$  mm Hg or diastolic blood pressure  $\geq 85$  mm Hg or undergoing drug treatment for hypertension, or antihypertensive drug treatment in a patient with a history of hypertension

4. Screening MRI-PDFF with  $\geq 10\%$  liver steatosis
5. Fasting serum LDL-C  $>100$  mg/dL at Screening
6. Women of childbearing potential (WOCBP) must have a negative serum pregnancy test (beta human chorionic gonadotropin) at Screening and must agree to use highly effective birth control throughout the study and up to 30 days after the last dose of study drug. Highly effective contraception measures include combined estrogen- and progestogen-containing hormonal contraception (oral, intravaginal, and transdermal), progestogen-only hormonal contraception associated with inhibition of ovulation (oral, injectable, and implantable), intrauterine device, intrauterine hormone-releasing system, bilateral tubal occlusion, vasectomized partner (only in the event that the vasectomized partner is the sole sexual partner of the WOCBP), and sexual abstinence (defined as refraining from heterosexual intercourse) only in the event that this is the preferred lifestyle of the patient.

Childbearing potential is defined as being fertile following menarche and until becoming postmenopausal unless permanently sterile (hysterectomy, bilateral salpingectomy, or bilateral oophorectomy).

A postmenopausal state is defined as no menses for  $\geq 12$  consecutive months without an alternative medical cause. A follicle-stimulating hormone level in the postmenopausal range will be used to confirm a postmenopausal state in women  $\leq 55$  years of age.

Men with partners who are WOCBP must either be surgically sterile or agree to use a barrier contraceptive for the duration of the study and up to 30 days after the last dose of study drug.

7. Be willing to maintain a stable diet and physical activity throughout the course of the study

### **7.2.2      Exclusion Criteria**

Patients who meet any of the following criteria will not be included in the study:

1. Women who are pregnant, breastfeeding, or plan to become pregnant during the study
2. Body mass index (BMI)  $<25 \text{ kg/m}^2$
3. Fibrosis-4 index (Fib-4)  $>2.6$
4. Any of the following laboratory abnormalities:
  - a. ALT  $>5 \times$  upper limit of normal (ULN) or AST  $>5 \times$  ULN
  - b. International normalized ratio (INR)  $\geq 1.3$ , unless on anticoagulant therapy
  - c. Total bilirubin  $>$ ULN, except with an established diagnosis of Gilbert's syndrome
  - d. Platelet count less than the lower limit of normal (LLN)
  - e. Creatinine clearance as calculated by the modification of diet in renal disease (MDRD) estimated glomerular filtration rate (eGFR) equation  $<60 \text{ mL/min}$

NOTE: Unless otherwise specified, repeat testing may be performed in consultation with the Medical Monitor.

5. Acute or chronic liver disease other than NAFLD/NASH including but not limited to the following:
  - a. Hepatitis B (as defined by the presence of hepatitis B surface antigen at screening) or hepatitis C (as defined by the presence of hepatitis C virus [HCV] antibody [anti-HCV]). Patients with positive anti-HCV who test

negative for HCV ribonucleic acid at screening will be allowed to participate in the study as long as there is evidence of viral negativity for a minimum of 12 months prior to screening)

- b. Evidence of autoimmune hepatitis
- c. History of primary biliary cholangitis, primary sclerosing cholangitis, Wilson's disease, homozygous alpha-1-anti-trypsin deficiency, hemochromatosis or iron overload, drug-induced or alcoholic liver disease, or known bile duct obstruction
- d. Suspected or proven hepatocellular carcinoma
6. Known history of human immunodeficiency virus
7. Medical history of liver cirrhosis
8. Clinical evidence of portal hypertension to include any history of ascites, hepatic encephalopathy, or presence of esophageal varices
9. Use of drugs historically associated with NAFLD (amiodarone, methotrexate, systemic glucocorticoids, tetracyclines, tamoxifen, estrogens at doses greater than those used for hormone replacement, anabolic steroids, or valproic acid) or other known hepatotoxins for >2 weeks in the year prior to screening
10. Use of the following medications:
  - a. GLP-1 agonists unless on a stable dose 3 months prior to liver biopsy or Screening
  - b. Ursodeoxycholic acid, thiazolidinediones, or obeticholic acid within 3 months prior to Screening
  - c. Statins and other lipid-modifying therapies must have been stable for  $\geq 3$  months prior to Screening
  - d. Oral antidiabetic drugs (other than those specifically excluded) must have been stable for  $\geq 3$  months prior to Screening

- e. Agents (including herbal over-the-counter weight-loss preparations) or medications known to significantly impact body weight within 3 months prior to Screening (e.g., sibutramine, phenetamine, and orlistat)
- 11. History of significant alcohol consumption, defined as an average of >20 g/day in female patients and >30 g/day in male patients, for a period of >3 consecutive months within 1 year prior to Screening, hazardous alcohol use (Alcohol Use Disorders Identification Test score ≥8), or an inability to reliably quantify alcohol consumption based upon judgment of the Investigator
- 12. Weight change ≥10% within the 6 months prior to Screening or ≥5% within the 3 months prior to Screening
- 13. Prior or planned (during the study period) bariatric surgery (e.g., gastroplasty, sleeve gastrectomy and roux-en-Y gastric bypass)
- 14. Type 1 diabetes by medical history
- 15. Uncontrolled Type 2 diabetes defined as hemoglobin A1c (HbA1c) >9.5% at Screening (patients with HbA1c >9.5% may be rescreened) or requiring oral diabetes medication dose adjustment >10% within 2 months prior to Screening
- 16. Clinical hyperthyroidism or hypothyroidism or screening hormone results pointing to thyroid dysfunction. Patients receiving dose-stable thyroid replacement therapy for ≥3 months prior to Screening will be allowed to participate as long as thyroid tests (thyroid-stimulating hormone/triiodothyronine/thyroxine) show that the patient is euthyroid
- 17. History of any condition causing malabsorption such as chronic pancreatitis, extensive bowel/small intestine surgery, celiac disease, or bile flow obstruction
- 18. History of any condition associated with acute or chronic diarrhea such as inflammatory bowel disease (IBD), functional diarrhea, irritable bowel syndrome (IBS) with predominant diarrhea, IBS with mixed bowel habits, or unclassified IBS
- 19. History of ischemic colitis

20. Uncontrolled hypertension (either treated or untreated) defined as systolic blood pressure >160 mmHg or a diastolic blood pressure >100 mmHg at Screening. A retest of blood pressure, (after establishing good blood pressure control within a reasonable period of time and up to the Baseline visit) is permissible at the discretion of the Investigator
21. History of New York Heart Association Class III or IV heart failure, or known left ventricular ejection fraction <30%
22. History of myocardial infarction, unstable angina, percutaneous coronary intervention, coronary artery bypass graft, or stroke or major surgery within 6 months prior to Screening
23. Active substance abuse within 1 year prior to Screening
24. Participation in an investigational new drug trial in the 30 days prior to Screening or within 5 half-lives of an investigational agent, whichever is longer
25. Malignancy within 5 years, except for basal- or squamous-cell carcinoma of the skin or carcinoma in situ of the cervix that has been successfully treated. Patients with a history of other malignancies that have been treated with curative intent and which have no recurrence within 5 years may also be eligible if approved by the Sponsor's Medical Monitor. Patients under evaluation for malignancy are not eligible
26. Patients with known intolerance to MRI or with conditions contraindicated for MRI procedures
27. Any other condition which, in the opinion of the Investigator, would impede compliance, hinder completion of the study, compromise the well-being of the patient, or interfere with the study outcomes

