### 5.2 Background

#### 5.2.1 Nonalcoholic Fatty Liver Disease (NAFLD) and Nonalcoholic Steatohepatitis (NASH)

Recent data suggest that bile acids may play an important role in NASH pathogenesis (Ferslew 2015; Aranha 2008; Puri 2018). Bile acids are signaling molecules involved in lipid, glucose, and energy homeostasis, which are metabolic pathways linked to NAFLD/NASH and comorbidities such as metabolic syndrome, obesity, and diabetes. Bile acids as well as free cholesterol, which is the precursor from which bile acids are synthesized, can act as lipotoxic agents that drive inflammation and fibrosis. Studies have shown that both serum and liver bile acids are increased in patients with NASH, and recent data have suggested that the presence and severity of NASH is associated with specific changes in circulating bile acids (Puri 2018). Thus, targeting of bile acid pathways has therapeutic potential in patients with NASH.

The enterohepatic circulation of bile acids plays a crucial role in whole body sterol balance. Bile acids are secreted to the intestine via the bile duct and then reabsorbed, mainly by a specific bile acid transporter located in the ileum (IBAT or ASBT) and delivered back to the liver, completing the enterohepatic circulation (Prawitt 2011).

Bile acid reabsorption from the intestine is a very efficient process where 95% of the secreted bile acids are reabsorbed and IBAT appears to be the major regulator of the bile acid pool in animals and humans. IBAT inhibitors reduce the reabsorption of bile acids from the ileum and prevent their return to the liver. The liver compensates for the decrease in bile acid levels by upregulating cholesterol 7 $\alpha$ -hydroxylase, the rate-limiting

enzyme for bile acid synthesis. This results in lower hepatic cholesterol levels and an increased number of low-density lipoprotein (LDL) receptors in the liver leading to reduced plasma low-density lipoprotein cholesterol (LDL-C; [Bertolotti 2003; Naoumova 1999]). Bile acids also positively regulate glucagon-like peptide-1 (GLP-1) levels via activation of TGR5 (Prawitt 2011; Schaap 2014). GLP-1 is an insulinotropic hormone but has many other roles, e.g., slowing gastric emptying and increasing satiety signals leading to weight loss (Andersen 2018).

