### **8.7 Concomitant Therapy and Prohibited Medications**

The Investigator will note all ongoing medication and any medication recently stopped (within 3 months prior to Visit 2) in the eCRF. At Visits 2 through 6, all changes in medication (stopping or starting new medication or changes in dose) will be recorded in the eCRF.

All medications taken by a patient within 3 months prior to the first intake of study drug are regarded as prior medication.

All medications taken by a patient on or after the first intake of study drug, and which continue to be taken during the study, are regarded as concomitant medication.

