## **9. ASSESSMENT OF EFFICACY**

### **9.1 Efficacy Endpoints**

#### **9.1.1 Primary Efficacy Endpoint**

The primary efficacy endpoint is the change from Baseline in serum LDL-C at Week 16.

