#### **9.1.2 Secondary Efficacy Endpoints**

Secondary efficacy endpoints include the following:

- Absolute change from Baseline to Week 16 in liver fat fraction (%) as measured by MRI-PDFF
- Absolute change from Baseline to Week 16 in total liver fat (mL) as measured by MRI
- Change from Baseline to Week 16, and Follow-Up in the following:
  - Serum ALT, AST, and gamma-glutamyl transferase
  - HDL-C, non-HDL-C, LDL-C/HDL-C ratio, and triglycerides
  - Total bile acids

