## **3.2 EFFICACY ANALYSES**

### **Primary Endpoint**

The primary efficacy endpoint for this study is the change from baseline in serum LDL-C at week 16.

Change from baseline in serum LDL-C will be analyzed by using an analysis of covariance (ANCOVA) after the missing data imputation. The ANCOVA model will include treatment group as a factor, baseline LDL-C and baseline LDL-C by treatment interaction values, and baseline **lipid lowering medications (Yes or No)** as covariates.

Serum LDL-C results and the change from baseline at each scheduled time point, along with the minimum and maximum post baseline value, will be summarized using descriptive statistics.

Box plots for serum LDL-C results absolute value and change from baseline overtime will be provided.

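### Exclusion 10c leaves stable bile acid sequestrant users eligible, and the SAP has no analysis that separates them from statin users

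*Protocol*

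**What the plan says.** **Mechanism.** Protocol 5.2.1 states that "IBAT inhibitors reduce the reabsorption of bile acids from the ileum and prevent their return to the liver". The liver responds by making more bile acid from cholesterol, LDL receptors increase, and plasma LDL-C falls.

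**Endpoints.** Protocol 9.1.1: "The primary efficacy endpoint is the change from Baseline in serum LDL-C at Week 16". Protocol 9.1.2 lists "Total bile acids" as a secondary endpoint. Protocol 9.1.3 lists C4 and FGF-19 as exploratory.

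**Eligibility (Protocol 7.2.2).** Criterion 10b bars "Ursodeoxycholic acid, thiazolidinediones, or obeticholic acid within 3 months prior to Screening". Criterion 10c reads "Statins and other lipid-modifying therapies must have been stable for" at least 3 months before Screening and carves out no class. Criterion 27 leaves to the investigator any other condition that would "interfere with the study outcomes", and names no drug.

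**On-study medication.** The title of Protocol 8.7 promises prohibited medications, but the section lists none. It says that "all changes in medication (stopping or starting new medication or changes in dose) will be recorded in the eCRF". SAP 2.2 counts prolonged use of disallowed medication as an important deviation, but no list of disallowed on-study drugs is given.

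**Analysis.**
- The SAP 3.2 primary endpoint text adds baseline lipid-lowering medication, Yes or No, to the ANCOVA. Step 5 of the imputation procedure and the sample ANCOVA code both omit it.
- The sensitivity MMRM for LDL-C includes the same Yes/No term.
- The secondary ANCOVA uses treatment and the endpoint's own baseline only.
- A lipid-lowering Y/N subgroup analysis is optional.
- SAP 3.1 summarises medications by ATC level and preferred term for each arm, with a subject-level listing.

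**The concern.** The trial tests whether interrupting bile acid return lowers LDL-C. In a patient who already takes a drug that interrupts the same return, that pathway may be partly engaged before Day 1. Such a patient may have less further LDL-C fall to show. Baseline total bile acids, C4 and FGF-19 may also sit apart from those of other patients. A stable dose removes drift over the study, but it does not remove a shared mechanism.

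The protocol already screens out some disturbances of bile acid handling: two drugs in 10b, and malabsorption and bile flow obstruction in exclusion 17. One reference cited in 5.2.1 reports, by its title, that C4 findings differed according to whether bile acid synthesis had been raised beforehand. That study concerned a different drug class and only its title is available here, but it points the same way.

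At stake are the size of the LDL-C estimate and the readability of the mechanism endpoints, in a trial with 23 patients per arm and no documented power margin.

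**Working it through.** **Inputs from the documents.** 46 patients, 23 per arm, with no effect size, SD or power behind the number (Protocol 11.1, SAP 1.3). Two-sided 5% tests (SAP 2.1).

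**Assumptions, none of them in the documents.** Sequestrants act on the bile acid return step. *k* is the number of users in the active arm, *f* the share of all patients who are users, and *b* the share of the drug effect lost in a user.

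**Step 1: is a stable user eligible?**

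| Text | Effect on a stable sequestrant user |
|---|---|
| 10b | Not named, so not barred |
| 10c | A lipid-modifying therapy stable for 3 months passes |
| Exclusion 27 | Investigator discretion only |
| 8.7 | Records medication changes and prohibits nothing |

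The user is eligible as written.

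**Step 2: direct attenuation.** Observed mean effect = full effect × (1 − k·b/23).

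| Active-arm users, k | Loss if b = 1 | Loss if b = 0.5 |
|---|---|---|
| 1 | 1/23 = 4.3% | 0.5/23 = 2.2% |
| 2 | 2/23 = 8.7% | 1/23 = 4.3% |
| 3 | 3/23 = 13.0% | 1.5/23 = 6.5% |

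This counts active-arm users only. A single user among all 46 has an even chance of being in that arm, so the expected loss is at most 1/46 = 2.2%.

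**Step 3: what that means for power.** The plan states no power figure to reproduce. For scale, the difference detectable with 80% power is d = (1.960 + 0.842) × √(2/23) = 0.826 SD. The diluted value is 0.826 × (1 − f·b), by normal approximation with the SD held fixed.

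| Share of users, f | Diluted d (b = 1) | Power, b = 1 | Power, b = 0.5 |
|---|---|---|---|
| 0 | 0.826 | 80.0% | 80.0% |
| 1 of 46 | 0.808 | 78.3% | 79.1% |
| 5% | 0.785 | 75.9% | 78.0% |
| 10% | 0.744 | 71.3% | 75.9% |
| 20% | 0.661 | 61.1% | 71.3% |

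**Step 4: does the Yes/No term repair it?** A main-effect covariate adjusts the level of the outcome. It cannot restore a treatment effect that differs between drug classes sharing one category. A simulation of 4,000 trials per scenario checked this, with half of patients assumed to be on lipid-lowering drugs, b = 1 and a full effect of −0.826.

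| f | Without Yes/No term | With Yes/No term | Leaving users out |
|---|---|---|---|
| 10% | −0.739 | −0.739 | −0.823 |
| 20% | −0.651 | −0.652 | −0.818 |

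The term changes nothing of note. Leaving users out recovers the effect in non-users, as it must under these assumptions.

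For total bile acids, C4 and FGF-19 the documents give no means or SDs, so the added variance cannot be sized.

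**The case against.** The other side has several sound points.

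- **No affected patient is shown.** The documents report no enrolled sequestrant user and no residual-response figure. A reader might infer that such patients did dilute the LDL-C effect and distort the bile acid endpoints. The documents support only that this could happen.
- **It is not bias.** A reader might infer that the comparison is tilted towards one arm. Randomisation prevents any systematic tilt. The ITT estimate remains valid for the mix of patients enrolled. What remains is attenuation relative to non-users, extra variance and possible chance imbalance at 23 per arm.
- **10b is not a pure bile acid list.** It also bars thiazolidinediones, and no rationale is given. Reading the absence of sequestrants as an oversight is therefore an inference.
- **Background therapy is a legitimate design choice.** Inclusion 5 requires LDL-C above 100 mg/dL at Screening, so every patient, treated or not, has residual LDL-C to lower.
- **The SAP does more than one covariate.** The MMRM carries the term, a Y/N subgroup is possible, and the ATC and preferred-term tables and listing would show any user. Total bile acids is adjusted for its own baseline, with a rank ANCOVA if assumptions fail. C4 and FGF-19 get per-patient plots.

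These points limit the size and certainty of the concern. They do not close the gap. Every planned adjustment or subgroup for lipid-lowering medication is Yes/No, and a listing shows a user without analysing the consequence.

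**Conclusion.** The gap in the eligibility text is real: a stable sequestrant user passes 10c although that class acts on the mechanism under test, and no planned analysis isolates the class. The consequence is conditional. It rests on general pharmacology outside the documents and on at least one user having enrolled.

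The loss is at most 4.3% of the LDL-C effect for each fully non-responding active-arm user, and about half that if half the response remains. One user among 46 costs at most about 2% of the effect in expectation and about 2 power points from the illustrative 80%. Larger losses need shares of users, such as 10% or 20%, for which the documents give no support.

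This is a cheap improvement to an exploratory study. It is not evidence that the primary comparison is unsound.

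**What to change.** 1. **Protocol 7.2.2.** The sponsor should reconcile 10b and 10c so that the treatment of bile acid sequestrants is explicit and consistent with the mechanism in 5.2.1. Which rule to adopt is a clinical decision and is not proposed here. SAP 1.0 is dated 07/06/2020 and the planned study period ended in Q2 2020, so for patients already randomised the practical remedy is in the SAP.
2. **SAP 3.1.** Before unblinding, flag baseline sequestrant users from the coded ATC and preferred-term data, meaning started before first dose and not stopped before it. Define the flag from the dates, because the SAP's definitions of prior and concomitant medication do not clearly place a drug begun before first dose and still ongoing with no stop date.
3. **SAP 3.2.** Prespecify a sensitivity analysis that repeats the LDL-C, total bile acid, C4 and FGF-19 analyses without flagged patients. Keep the full ITT analysis as primary. If nobody is flagged, one sentence in the report closes the question.
4. **SAP 2.2.** Do not add sequestrant use to the per-protocol deviations. 10c permits it, so these patients complied with the protocol. State what counts as disallowed medication.
5. **SAP 3.2, Step 5 and sample code.** Make these agree with the primary endpoint text on the lipid-lowering term.

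**Cost.** A few SAP lines and one rerun, with no new data. The flag uses pre-randomisation information, so the remaining comparison is still randomised. Precision falls slightly in that run only: leaving out 3 of 46 patients widens the standard error by about √(46/43) − 1 = 3.4%.
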